10.4.2. Prospective cohort

For subjects who have been pathologically confirmed prostate cancer with clinical stage T1-T2, will receive the treatment of spaceOAR in hospital in BOAO. The radiotherapy plan will be made by radiotherapist according to clincial guideline and conditions of subjects.

- 1) Informed consent

Study objective, schedule and visits will be informed to subjects fully, and the ICF will be signed voluntarily.

2) Before procedure

The data below will be collected, such as demographics, physical assessment (height, weight), clinical diagnosis and clinical stage, Gleason score, PSA, CT, MRI and other related examinations, medical history, urinary history and surgery history etc. IPSS score will be collected, if any, and questionnaires of EPIC and quality of life (EQ-5D-5L) will be completed. (Clinical diagnosis and clinical stage, Gleason score, CT and MRI from other hospital within 30 days before procedure are allowed.)

3) Procedure

According to regulations of licenced medical device in Hainan, subjects will go to BOAO to receive treatment of SpaceOAR. SpaceOAR is injected between the prostate and rectum via TRUS .

All administration of SpaceOAR hydrogel will be conducted by trained urologists at the hospital in Boao.

Procedure information will be collected, such as anesthesia, SpaceOAR dosage, intraoperative device usage, device defects (if any), adverse events, complications, etc.

4) Post procedure

CT and MRI will be conducted in 10 days post procedure. AE and device deficiency, as applicable, will be assessed. CT and MRI will be conducted for all subjects to complete radiotherapy planning. MRI in other hospital will be allowed to avoid duplication assessment.

5) 30 days follow up visit post procedure

This visits will be conducted via phone, health status and concommit medication will be inquired, AE and device deficiency (if any) will be assessed and collected.

10.5. Study Completion

This is a real world study on licenced medical device. When last subject complete 30 days (± 7 days) follow up visit, and all data is collected, this study will come into end.

10.6. Source Documents

It is preferable that original source documents are maintained, when available. In lieu of original source documents, certified copies are required to be maintained. A certified copy is a copy (irrespective of the type of media used) of the original record that has been verified (i.e., by a dated signature or by generation through a validated process) to have the same information, including data that describe the context, content, and structure, as the original.

11. Statistical Considerations

11.1. Endpoints

11.1.1. Primary Effectiveness Endpoint

The primary endpoint is The distance between the posterior prostatic capsule and anterior rectal wall post SpaceOAR hydrogel administration.

11.1.1.1. Hypotheses

This is a retrospective and prospective, single arm study with a performance goal approach for the primary effectiveness endpoint. The primary effectiveness endpoint is the distance between the posterior prostatic capsule and anterior rectal wall post SpaceOAR hydrogel administration. As this is real word study with less strict I/E criteria, the performance goal was set as 7.5mm, based on the rationales in the SpaceOAR EU pilot study, in which the creation of at least a 7.5mm space criterion was developed in consult with Augmenix's Scientific Advisory Board (a panel that consists of board-certified radiation oncologists). If the two-sided 95% Lower Confidence Interval (LCI) of distance calculated is greater than PG, the study primary effectiveness endpoint will be met.

11.1.1.2. Sample Size

The distance was 12.58 ± 3.88 mm (N=147) in the Space OAR hydrogel pivotal study in USA (IDE study), and it was 15.5 ± 5.7 mm (N=48) in pilot study in EU. For the sample size estimation, a distance between prostate and rectum of 13 mm is expected with a standard deviation of 5.7 mm.

The sample size is calculated according to below formula:

$$n = \frac{(Z_\alpha + Z_\beta)^2 \sigma^2}{\delta^2}$$

n is sample size, PG is assumed as 7.5mm, 13mm is expected distance between prostate and rectum, $\delta = 5.5$ mm, $\sigma = 5.7$ mm, $\alpha = 0.025$, $\beta = 0.1$ (power=90%). Therefore, a sample size of 14 subjects will provide more than 90% power.

To account for potential missing data in this retrospective and prospective study, a final sample size will be up to 20 subjects.

11.2. General Statistical Methods

11.2.1. Analysis Sets

This study is a retrospective and prospective, real world study, in which subjects who received the treatment of spaceOAR in hospital in BOAO will be enrolled. The efficacy analysis set includes subjects with available distance between prostate and rectum measured from MRI post procedure. The safety analysis set includes all subjects who have received treatment of SpaceOAR in hospitals in Hainan BOA.

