The SpaceOAR System has been marketed in Australia, Canada, Japan, Europe and USA. A pilot study of SpaceOAR System in Europe enrolled 52 subjects. The objective of the Pilot Study was to evaluate the initial safety and effectiveness of SpaceOAR System when it is injected between the rectum and prostate in adult men undergoing external beam radiation therapy for treatment of low-to-mid risk prostate cancer. The space creation effect of SpaceOAR hydrogel was assessed via co-primary effectiveness endpoints. Analysis of the endpoints for the Per Protocol Population showed that³⁴, Functional Success, defined as the creation of at least 7.5 mm space between the prostate (Mid-gland) and rectum measured on CT or MRI, was achieved in 46 of 48 subjects (95.8%). Clinical Success, defined as reduction in radiation dose to the anterior rectum as measured by a 25% or greater reduction in rV70 (i.e., the percent volume of the rectum receiving at least 70 Gy) was achieved in 44 of 46 subjects (95.7%). There were no unanticipated adverse events associated with the SpaceOAR System procedure or the SpaceOAR hydrogel. These results from the Pilot Study established initial safety and performance for use of the SpaceOAR System as a means to physically separate the rectum from the prostate and reduce the rectal radiation dose.

The pivotal study of SpaceOAR System in USA aimed to evaluate the safety and effectiveness of the SpaceOAR System when it is used in patients with a pathologically confirmed diagnosis of clinical stage T1 or T2 prostate cancer who were indicated for a course of IMRT. 222 eligible subjects were enrolled and were randomized (2:1) to the Treatment group (SpaceOAR System) or Control group after successful fiducial marker placement. The study showed that hydrogel placement success rate was 99%; Perirectal spaces were 12.6 ± 3.9 mm and 1.6 ± 2.0 mm in the spacer and control groups, respectively. There were no device-related adverse events, rectal perforations, serious bleeding, or infections within either group. The reduction of rectal V70 in treatment group was significantly more than control group (12.4% to 3.3%, P<.0001). Overall acute rectal adverse event rates were similar between groups, with fewer spacer patients experiencing rectal pain.

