6.2. Study endpoints

6.2.1 Primary endpoint

6.2.1.1 Primary effectiveness endpoint

The distance between the posterior prostatic capsule and anterior rectal wall post SpaceOAR hydrogel administration.

Measurement: The distance between the posterior prostatic capsule and anterior rectal wall is measured on the axial image slice closest to halfway between apex and base, from posterior edge of prostate to inner rectal wall via MRI.

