10.1. Data Collection

The data collection schedule is shown in table 10-1 .

Table 10-1:Data Collection Schedule

Procedure/Assessment	Before procedure	Procedure	Post procedure	30 days post procedure (± 7 days)
Informed consent[#]	X			
Demographics	X			
Physical assessment, including weight and height	X			
Clinical diagnosis and clinical stage of tumor、 Gleason score	X			
Medical history (General disease, genitourinary history / treatment history)	X			
Questionnaires (IPSS, EPIC, QoL)	X			
Administration of SpaceOAR		X		
PSA	X			
CT&MRI[*]	X		X	
Concomitant medication		X	X	
Adverse event		X	X	X
Device Deficiency		X	X	X
PD[#]	X	X	X	X

Note:# only for patients enrolled prospectively;

*MRIs conducted in other hospital are allowed, ie, MRI completed in 30 days before procedure and in 10 days after procedure will be allowed in this study. MRI is required for patients with prostate cancer who receive radiotherapy; technical success and distance between the prostate and rectum will be evaluated based on MRI image.

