10.4.1. Retrospective cohort

For subjects who have received treatment of SpaceOAR, the relevant clincial data below will be collected and be entered in EDC.

- Before procedure: data at baseline will be collect, eg. demographics, physical assessment (height, weight), clinical diagnosis and clinical stage, Gleason score, PSA, CT, MRI and other related examinations, medical history, urinary history and surgery history etc.(Clinical diagnosis and clinical stage, Gleason score, CT and MRI from other hospital wthin 30 days before procedure are allowed, as applicable.)
- Procedure : collecting procedure information such as anesthesia, SpaceOAR dosage, intraoperative device usage, device defects (if any), complications, etc.
- Post procedure: CT and MRI of subjects will be collected retrospectively; Adverse events and device deficiency within 30 days post procedure(if any) will be retrospectively collected.(CT and MRI performed in 10 days after surgery are allowed.)

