4 GENERAL STATISTICAL METHODS

4.1 Analysis Sets

This study is a retrospective and prospective, real world study, in which subjects who received the treatment of SpaceOAR in hospital in BOAO will be enrolled.

The efficacy analysis set includes subjects with available distance measurement between prostate and rectum measured from MRI post procedure.

The safety analysis set includes all subjects who have received treatment of SpaceOAR in hospitals in Hainan BOAO.

All enrolled set: Retrospective subjects, who have already received the SpaceOAR treatment, are enrolled when they meet the inclusion criteria. Prospective subjects, who will receive the SpaceOAR treatment, informed consent will be performed for enrollment.

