4.2 Control of Systematic Error/Bias

All patients who receive the treatment of SpaceOAR in hospital in BOAO will be enrolled during the study period to minimize selection bias.

4.3 Method of handling missing, incorrect data (including subjects withdrawal and lost to follow-up) and unreasonable data

Missing data will be excluded for primary analysis in this small sample size study. Incorrect and unreasonable data will be clarified before database lock. Imputation with mean or median where applicable for continuous variable, and tipping point analysis where applicable for categorical variable might be conducted for sensitivity analysis. Visit-wise mean and LOCF imputation methods will be used for missing values.

Missing Event Dates Considerations:

For adverse events with missing event date (i.e., mm/dd/yyyy), the safety and/or data management representatives will query sites for missing data. In the event that the date for adverse event is missing at the time of analysis, please reference Section 7.4 for the missing/partial date handling rules.

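### The SAP 4.3 fill-in rules are unsound for a missing post-procedure distance, while post-procedure CT that could serve as a sensitivity check goes unused

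*Protocol*

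**What the plan says.** **Instrument.** Protocol 6.2.1.1 measures the primary distance on the mid-gland axial slice, "from posterior edge of prostate to inner rectal wall via MRI". The footnote to Table 10-1 agrees: "technical success and distance between the prostate and rectum will be evaluated based on MRI image". Protocol 11.2.1 restricts the efficacy set to men with such a measurement: "The efficacy analysis set includes subjects with available distance between prostate and rectum measured from MRI post procedure". SAP 4.1 repeats the rule: "The efficacy analysis set includes subjects with available distance measurement between prostate and rectum measured from MRI post procedure".

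**CT.** CT and MRI share one row of Table 10-1, before and after the procedure. For the retrospective cohort (Protocol 10.4.1), "CT and MRI of subjects will be collected retrospectively"; for the prospective cohort (10.4.2), "CT and MRI will be conducted for all subjects to complete radiotherapy planning". Both sections give a 10-day post-procedure window. Neither document uses the CT in any endpoint or analysis.

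**Origin of 7.5 mm.** Protocol 11.1.1.1 takes the performance goal from the EU pilot. Protocol 4.1 reports that study's Functional Success criterion as "creation of at least 7.5 mm space between the prostate (Mid-gland) and rectum measured on CT or MRI".

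**Missing data.** The primary analysis leaves missing values out (Protocol 11.2.3, SAP 4.3). As an optional sensitivity analysis SAP 4.3 offers "Imputation with mean or median where applicable for continuous variable", with a tipping-point analysis for categorical variables. Its next sentence says that visit-wise mean and LOCF will be applied to missing values. It does not say which rule governs the distance.

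**The concern.** A sensitivity analysis for missing distances should show whether the result survives if the missing men did worse. A mean fill cannot do this. It reproduces the observed mean by construction, counts invented values as data, and so looks more secure than the complete-case result it is meant to test. The distance has one scheduled post-procedure assessment, so a visit-wise mean is the same fill. LOCF errs the other way: the only earlier value available is the gap before injection.

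Missing distances are foreseeable. Retrospective enrolment needs a complete procedure record (Protocol 9.1, 10.2), not an MRI. In that cohort a test not done is not a deviation (Protocol 14), and enrolment is raised to as many as 20 to allow for missing data (11.1.1.2). Men without an MRI may differ from those with one. Where such a man has a planning CT, an actual reading of the gap may be available, and the plan passes it over for a constant.

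**Working it through.** **Inputs.** Expected mean 13 mm, SD 5.7 mm, goal 7.5 mm, one-sided 0.025, required n = 14, enrolment up to 20 (Protocol 11.1.1.2, SAP 3.1.2); one-sample t-test (SAP 3.1.3).

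**1. The plan's own figure.** The printed formula gives (1.960 + 1.282)² × 5.7² / 5.5² = 11.29, so 12. The exact t-test first reaches 90% power at n = 14 (91.5%). The stated 14 is therefore confirmed for the test the SAP uses. Power at n = 20 is 98.3%, so losing six men leaves it above 90%. Power is not the issue.

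**2. Mean fill.** With N = 20, m values filled and n = N − m observed, the filled SD is 5.7 × √((n − 1)/(N − 1)).

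For m = 6:
- Filled SD = 5.7 × √(13/19) = 4.71 mm.
- Half-width, filled: 2.093 × 4.71/√20 = 2.21 mm.
- Half-width, complete-case: 2.160 × 5.7/√14 = 3.29 mm.
- True one-sided error: the filled standard error is 1.054 mm, against 1.523 mm for the 14 real values. The nominal cut-off 2.093 then corresponds to 2.093 × 1.054/1.523 = 1.449 on 13 df, which is exceeded with probability 8.6%.

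| Missing of 20 | Half-width, complete-case (mm) | Half-width, mean-filled (mm) | True one-sided error of filled test |
|---|---|---|---|
| 2 | 2.84 | 2.52 | 3.9% |
| 4 | 3.04 | 2.37 | 5.9% |
| 6 | 3.29 | 2.21 | 8.6% |

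The table is for a mean fill with values missing at random. A median fill behaves similarly when the median is close to the mean.

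**3. Effect at the planned mean.** With six missing and an observed mean of 13 mm, the lower limit is 13 − 3.29 = 9.71 mm complete-case and 13 − 2.21 = 10.79 mm filled. Both exceed 7.5 mm.

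**4. LOCF.** The documents give no pre-injection gap for this population. As an assumed stand-in I use 1.6 mm, the pivotal study's control-group mean (Protocol 4.1). Carrying 1.6 mm forward, with the observed men at 13 mm, gives lower limits of 8.85 mm (2 missing), 7.49 mm (4) and 6.24 mm (6). The endpoint would fail from four missing, purely because an untreated gap was entered as a treated one.

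**5. How small the missing gaps must be.** Assume six missing men with true mean x and within-group SD 5.7, against 14 men at 13 mm. The all-subject variance is [18 × 5.7² + (14 × 6/20)(13 − x)²]/19.
- x = 9: mean (14 × 13 + 6 × 9)/20 = 11.8; SD √[(584.82 + 67.20)/19] = 5.86; lower limit 11.8 − 2.093 × 5.86/√20 = 9.06 mm, met.
- x = 5: mean 10.6; SD √[(584.82 + 268.80)/19] = 6.70; lower limit 7.46 mm, missed. Complete-case (9.71) and mean-filled (10.79) would both report success.

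**The case against.** The strongest reply has five parts.

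- **MRI-only is a consistent, prespecified definition.** This stands. A reader might infer that the MRI restriction is an error or a contradiction. It is neither: the efficacy set follows from the endpoint, and CT has its own stated purpose in radiotherapy planning.
- **The CT-only man may not exist.** MRI is planned for everyone, outside-hospital MRI is accepted, and a man whose records are incomplete may lack both scans. This stands. A reader might take 6 of 20 (30%) as the affected group, but it is the overall missing-data allowance. The documents give no CT-only count.
- **The planned methods are not blind to poor outcomes.** LOCF pulls towards failure, and the optional tipping-point analysis could be applied to Functional Success at the same 7.5 mm threshold. This stands in part: one cannot say that the plan could never reveal selective loss. But LOCF would do so with a value that is not a post-injection measurement, and no tipping-point analysis is offered for the primary, continuous distance.
- **CT and MRI are not shown to be interchangeable.** This stands. The pilot is a different study, and the protocol gives neither its CT/MRI split nor agreement data. CT therefore belongs in a sensitivity analysis only.
- **The result is robust at the planned effect.** This also stands, as steps 3 and 5 show.

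**Conclusion.** The point holds as a low-cost improvement to the sensitivity analysis. The primary analysis is sound and should stay on MRI. The fill-in rules in SAP 4.3 are not fit for the post-procedure distance: a mean-type fill understates uncertainty (with 6 of 20 missing, half-width 2.21 mm against 3.29 mm and one-sided error about 8.6%), and LOCF may substitute an untreated gap. These figures assume SD 5.7 mm, 20 enrolled and a t-test on the filled data. The number of CT-only men is unknown; 0 to 6 of 20 is an assumed range.

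A reader might infer that the study's conclusion is in danger. The documents do not support that. On complete-case data the endpoint would be wrongly declared met only if the missing men had much smaller gaps, such as six averaging 5 mm against 13 mm.

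**What to change.** Amend SAP 4.3 before the primary analysis, as SAP 5.3 allows:

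1. Exclude the post-procedure distance from the mean/median, visit-wise mean and LOCF rules. Keep the complete-case MRI analysis as primary.
2. As sensitivity analysis only, for treated subjects without a post-procedure MRI, use the mid-gland distance on the post-procedure CT from the same 10-day window.
3. Report the paired CT-minus-MRI difference in subjects with both scans, so that any offset is visible when item 2 is read.
4. For subjects with neither scan, apply a tipping-point analysis to the distance itself: lower their assumed mean, keeping a realistic within-group spread, until the lower limit reaches 7.5 mm, and report that value.

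The cost is SAP wording and up to about 20 extra measurements on existing images, with no new scan or visit. The documents name no reader for the distance, so the SAP should say who makes the CT measurements. The downside is that tissue boundaries may be less clear on CT than on MRI, which is why it stays out of the primary analysis.

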11.2.2. Control of Systematic Error/Bias

All patients who receive the treatment of SpaceOAR in hospital in BOAO will be enrolled at a given time, no cherry-pick patients and data to reduce select bias.

11.2.3. The method of handling missing, incorrect data(including subjects withdrawal and lost to follow-up) and unreasonable data

Missing data will be excluded for primary analysis in this small sample size study. Incorrect and unreasonable data will be clarified before database lock. Imputation where applicable for continuous variable, and tipping point analysis where applicable for categorical variable might be conducted for sensitivity analysis.

11.3. Data Analyses

Descriptive statistics will be used to summarize the study endpoints, such as distance between the posterior prostatic capsule and anterior rectal wall post SpaceOAR hydrogel administration, functional success. Continuous variables will be tabulated with mean, median, standard deviation, minimum, maximum. Categorical variables will be tabulated with frequencies, percentages along with the 95% confidence intervals.

This study may allow explorative statistics based on collected data, including but not limited to: risk factors associated with functional failure.

There is no formal interim analysis, but a descriptive summary will be made during the study, if needed.

Any statistical analysis change will be added in statistical analysis plan before data analysis.

12. Data Management

12.1. Data Collection, Processing, and Review

Subject data will be recorded in a limited access secure electronic data capture (EDC) system.

The clinical database will reside on a production server hosted by Medidata EDC System. All changes made to the clinical data will be captured in an electronic audit trail and available for review by BSC or its representative. The associated Rave software and database have been designed to meet regulatory compliance for deployment as part of a validated system compliant with laws and regulations applicable to the conduct of clinical studies pertaining to the use of electronic records and signatures. Database backups are performed regularly.

The Investigator provides his/her electronic signature on the appropriate electronic case report forms (eCRFs) in compliance with local regulations. A written signature on printouts of the eCRFs must also be provided if required by local regulation. Changes to data previously submitted to the sponsor require a new electronic signature by the Investigator acknowledging and approving the changes.

Visual and/or electronic data review will be performed to identify possible data discrepancies. Manual and/or automatic queries will be created in the Medidata EDC system and will be issued to the site for appropriate response. Site staff will be responsible for resolving all queries in the database.

All access to the clinical database will be changed to “Read only” after all data is either “Hard Locked” or “Entry Locked”. Once acceptance of the final report or finalization of publications (as applicable) is received, final database storage and archiving activities can begin. Once all of the closeout activities are completed a request to IT is submitted to have the “Database Locked” or Decommissioned and all database access revoked.

12.2. Data Retention

The Principal Investigator or his/her designee or Investigational site will maintain all essential study documents and source documentation that support the data collected on the study subjects in compliance with applicable regulatory requirements. Documents must be retained for 10 years after the formal discontinuation of the clinical investigation of the product or retained for a long time in accordance with site’s requirements. These documents will be retained by BSC until the product/device is no longer in use in compliance with local regulations.

The Principal Investigator or his/her designee will take measures to prevent accidental or premature destruction of these documents. If for any reason the Principal Investigator or his/her designee withdraws responsibility for maintaining these essential documents, custody must be transferred to an individual who will assume responsibility and BSC must receive written notification of this custodial change. Sites are required to inform Boston Scientific in writing where paper or electronic files are maintained in case files are stored off site and are not readily available.

13. Amendment

The investigator should adhere to study protocol approved by EC. Any Amendment to the protocol (management information or study process modification, etc.) should be completed and reviewed by the sponsor during the study, then should be submitted to the EC for approval via the investigator. Only the amendment of protocol is approved by EC, the amended protocol should be implemented.

14. Deviations

An Investigator must not make any changes or deviate from this protocol, except to protect the life and physical well-being of a subject in an emergency. An investigator shall notify the sponsor and the reviewing IRB/EC, and the regulatory authority if applicable of any deviation from the investigational plan to protect the life or physical well-being of a subject in an emergency, and those deviations which affect the scientific integrity of the clinical investigation. Such notice shall be given as soon as possible, but no later than 5 working days after the emergency occurred, or per prevailing local requirements, if sooner than 5 working days.

All deviations from the investigational plan, with the reason for the deviation and the date of occurrence, must be documented and reported to the sponsor using EDC. Sites may also be required to report deviations to the EC, and the regulatory authority, per local guidelines and national/government regulations.

Deviations will be reviewed and evaluated on an ongoing basis and, as necessary, appropriate corrective and preventive actions (including but not limited to EC/regulatory authority notification, site re-training, or site discontinuation/termination) will be put into place by the sponsor.

Considering that this study is a prospective and retrospective, real world study which is based on the 'pilot program' of licensed medical device, only collecting data, no intervention.

For data retrospectively collected, there is an chance of missing data, so missing data and undo test is not deemed to be deviations.

For prospective enrolled subjects who has signed ICF, Deviations must be recored, including but not limited to informed consent, inclusion criteria, follow-up visit etc.

15. Compliance

